4.4.8.3. Measurement of Sample Based Outcomes

In the Mortality and Resistance Trial, 150 AMR communities from the Dosso region will be randomly selected from the pool of eligible communities and followed to monitor antimicrobial resistance. Samples will be collected in a random subset of communities at baseline and in all 150 AMR communities after 2 years of distributions. For primary outcomes, samples will be processed from a subset of 150 communities.

In each of the selected Mortality/Resistance Trial communities, 30 children aged 1–59 months,

30 children aged 7–12 years, and 30 caregivers/guardians of eligible children will be randomly selected for additional monitoring. Nasopharyngeal samples will be collected from all sampled individuals. From children aged 1–59 months, rectal swabs, RDT, and dried blood spots will also be collected. In the sample of children aged 1–59 months, 10 children will be randomly selected for an additional nasopharyngeal swab which will be used for phenotypic testing. Samples will be collected at baseline and after 2 years of distributions.

To randomly select individuals for population-based monitoring in the Mortality/Resistance Trial, census data will be used. In the 150 Dosso communities selected for additional monitoring, the baseline and 24-month census will be separate from treatment and will include data collection on children aged 7–12 years old. The random samples of children in both age groups and caregivers/guardians will be selected from the census. To ensure that samples are collected on 30 individuals in each group, 50 children in both age groups and 50 caregivers/guardians will be randomly selected from the census data.

60 previously untreated communities will be incorporated into the Mortality/Resistance Trial in Round 4 and will receive rectal swab baseline collections. This is to account for rectal swab baseline samples collected in Round 1 that were damaged and unusable. 1 rectal swab will be collected from 30 children aged 1–59 months per community. Samples from community latrines and chicken feces will also be collected when available from the homes of the 30 children selected for this sample collection.

Environmental samples will be taken from communities and households from which participants were selected for data collection at baseline and 24 months. Latrine and water samples will be taken at the community level, and animal feces, stored water, and dirt samples will be taken at the household level.

Once the census is complete and the sample is generated, the study team will work with a local mobilizer to invite the sampled group to a central location in the community for sample collection. Samples will be collected by trained personnel and linked to census data through bar codes. Once sample collection is complete, the census team or community health workers will visit the study community to complete treatment for that round.

During collection, samples will be stored at ambient temperature or on ice at 4°C. At the end of each collection period, samples will be transported to a location near the sampled community with facilities to store samples at -20°C as required or directly to CRISP each day. At the end of the collection period, all samples will be transferred to a central storage location at CRISP in Niamey stored at -20°C as required until processed or shipped to UCSF for processing. Refer to Sample Collections Procedures and the Laboratory Procedures for full details.

All the same procedures will be followed for the additional communities that will be added from MORDOR.

4.4.8.4. Measurement of Additional Outcomes

Data on other programs that include the distribution of antibiotics in the study area will be collected. Seasonal Malaria Chemoprevention (SMC) implementation and coverage data will be collected from SMC implementers at the district and community level during the study. Trachoma distributions will be tracked, and prior distributions recorded for each community through communications with PNSO.

4.4.8.5. Data Collection and Management

All study personnel who assess outcomes will attend intensive, two-day training sessions prior to conducting study procedures. Training will include operation of the mobile device, data collection through the mobile application or on paper, and the study protocol and procedures.

Where possible, data will be collected electronically using a custom-designed mobile census application (CommCare, Dimagi) on mobile devices and uploaded regularly to a secure, cloud-based server. Where possible, data will be uploaded in real time using the cellular network, or weekly or monthly at a central site with strong Wi-Fi or cellular connection. In the Delivery Trial and Programmatic Trial communities, data on intervention administration will be recorded by community health workers on paper forms, and later entered electronically.

Mobile devices will be accessed via unique usernames and passwords. Mobile devices will be stored in locked offices with electricity for charging.

Validation will be used in development of the data collection forms to ensure to a large extent that there are no inconsistencies or invalid data. Data management teams in Niger and at UCSF will monitor data collection in real time daily. Progress and quality control reports will be prepared and distributed to investigators weekly.

Study participants will be assigned unique identification numbers that do not contain identifying information, which will be used to link data across databases and will be the only identifier shared in de-identified datasets.

The total number of all infectious and cause-specific CSI visits will be collected using data available from the Niger Ministry of Health.

Refer to the Data Monitoring Plan for full details.

4.4.8.6. Statistical Analysis Plan

Refer to the trial's Statistical Analysis Plan (SAP) for complete details

4.4.8.7. Quality Control and Monitoring

All study personnel will be trained on standardized study procedures for data collection before each round of study activities begin. A team of supervisors in Niger will monitor study personnel collecting data weekly, and the UCSF team will conduct biannual study monitoring visits. Weekly data monitoring reports will be distributed to the study team, with a detailed section on inconsistencies, errors, and missing data to be resolved by the data teams.

4.5. Delivery Trial

4.5.1. Trial Design

From the same pool of eligible communities, 160 communities in Dosso will be randomly selected for participation in one of two Delivery Trials:

In Delivery Trial I, 80 communities in Dosso will be randomly selected for participation in a 2-arm trial that will compare coverage, costs, and other implementation outcomes between fixed-point delivery and door-to-door delivery of azithromycin by community health workers to children

1–59 months of age.

In Delivery Trial II, 80 communities in Dosso will be randomly selected for participation in a 2-arm trial that will compare costs and other implementation outcomes between treating eligible children 1–11 months of age to treating eligible children 1–59 months of age. The intervention delivery method for all communities will be informed by Delivery Trial I.

4.5.2. Eligibility

Intervention

At the community-level, eligibility includes:

Inclusion criteria:

- Location in Dosso
- Population 250 to 2,499*
- Distance > 5 km from district headquarters town
- Distinguishable from neighboring communities
- Verbal consent of community leader(s)

Exclusion criteria:

- Inaccessible or unsafe for study team
- “Quartier” designation on national census

*Population size as estimated from the most recent national census or projections

At the individual-level, eligibility includes:

Inclusion criteria:

- Age 1–59 months or 1–11 months depending on arm allocation
- Primary residence in a study community
- Verbal consent of caregiver/guardian for study participation

Exclusion criteria:

- Known allergy to macrolides

4.5.3. Randomization, Adaptation, and Masking

4.5.3.1. Randomization

The randomization unit for these trials will be the *grappe*, which is the smallest health care unit administratively defined in Niger, hereafter referred to as “community.”

Delivery Trial I communities will be randomized in a 1:1 fashion to the following 2 arms:

- **Azithro 1–59 fixed point:** azithromycin distribution to children 1–59 months of age using a fixed-point delivery approach via existing community health workers
- **Azithro 1–59 door-to-door:** azithromycin distribution to children 1–59 months of age using a door-to-door delivery approach via existing community health workers

Delivery Trial II communities will be randomized in a 1:1 fashion to the following 2 arms:

- **Delivery azithro 1–11:** azithromycin distribution to children 1–11 months of age using a door-to-door delivery approach via existing community health workers
- **Delivery azithro 1–59:** azithromycin distribution to children 1–59 months of age using a door-to-door delivery approach via existing community health workers

4.5.3.2. Adaptation

The randomization sequence will be generated by the trial biostatistician at UCSF.

The Delivery Trial communities will not undergo adaptation during the Delivery Trial period and may be included in the adaptation or programmatic trial after the Delivery Trial is completed.

Refer to the trial's Statistical Analysis Plan (SAP) for complete details of the adaptive randomization algorithm.

4.5.3.3. Masking

In the Delivery Trial, participants, implementers, and outcome assessors will not be actively masked from the delivery approach given the nature of the intervention. Data analysts will be masked.

4.5.3.4. Interventions

Please refer to Section 4.4.3.4.

4.5.3.5. Dosage Information

Azithromycin or placebo will be administered as a single dose, in oral suspension form for children, of 20 mg/kg in children (up to the maximum adult dose of 1 g).

In the Delivery Trials and Programmatic Trial, the dose will be calculated by age for children aged 1–11 months. Aged-based dosing will be implemented as follows:

- 2 ml of azithromycin for children aged 1–2 months
- 4 ml of azithromycin for children aged 3–11 months

For children 12–59 months of age, height-based dosing will be used via height-stick approximation as currently performed by Niger's trachoma program.

Both dosing cups and syringes will be used to administer treatment. For children too young to drink out of a dosing cup, a 1 ml or 5 ml syringe will be used, and the calculated dose will be rounded upwards to the nearest 0.2 ml.

4.5.3.6. Side Effects

Please refer to Section 4.4.3.6.

4.5.3.7. Study Medication Storage and Accountability

Please refer to Section 4.4.3.7.

4.5.3.8. Medication Quality Control

Please refer to Section 4.4.3.8.

4.5.4. Outcomes

4.5.4.1. Delivery Trial I Primary Outcomes

- Treatment coverage as defined by the number of doses of azithromycin administered and recorded by community health workers divided by the eligible population as determined by a post-distribution census in each community after a single distribution.

4.5.4.2. Delivery Trial I Secondary Outcomes

- Program costs as captured by routine administrative data collection during the study period and by micro-costing activities
- Cost-effectiveness measured by estimated program costs and using measured mortality and estimated DALYs as the effectiveness outcome, compared across arms.
- Estimated national-scale effects (health and cost) of scaling up each strategy.
- Other implementation outcomes defined in the Proctor Outcomes Framework,¹³ including feasibility and acceptability, as captured during routine administrative and monitoring data collection during the study period and by stakeholder interviews at the participant, community, and health system levels after one round of distributions (Table 3)
- Treatment coverage as defined by projections using national and study census data collection as well as satellite imagery

4.5.4.3. Delivery Trial II Primary Outcomes

- Cost per dose delivered. Program costs will be captured by routine administrative data collection during the study period and by micro-costing activities. Doses delivered will be recorded by community health workers using paper data collection forms and entered electronically by the supervisor team.

4.5.4.4. Delivery Trial II Secondary Outcomes

- Treatment coverage as defined by the number of doses of azithromycin administered in each community divided by the total eligible population, which will be determined in several ways: using the recorded number of eligible children from the community health workers, using a pre-treatment census of eligible children, using self-reported coverage recorded during the post-treatment survey, and the administrative estimates of the eligible population from the health centers. The number of eligible children recorded by community health workers will be used for the main analysis with the others included as sensitivity analyses, and a separate analysis will be done to compare the 4 methods.
- Other implementation outcomes defined in the Proctor Outcomes Framework, including feasibility and acceptability, as captured during routine administrative and monitoring data collection during the study period and by stakeholder interviews at the participant, community, and health system levels after one round of distributions.

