4.5.8.2. Measurement of Implementation Outcomes

In the Delivery Trial, existing community health workers will be trained to distribute azithromycin to children 1–59 months of age or 1–11 months of age every 6 months. In communities randomized to fixed-point delivery, community health workers (CHWs) will work with community leaders to identify a central location, date, and time for delivery. Mobilizers in each community will be engaged to publicize the intervention. In communities randomized to door-to-door delivery, CHWs will visit every household in the community. In both sets of communities, CHWs will determine eligibility, obtain informed consent, administer treatment, and record treatment administration on paper data collection forms. For eligible children in Delivery Trial I, the dose will be determined via weight using a hanging scale for children under 12 months of age or height-stick approximation for children 12 months and older using the Niger trachoma program's height stick. For eligible children in Delivery Trial II, the dose will be determined via age for children under 6 months of age or height-stick approximation for children 6 months and older using the Niger trachoma program's height stick. Treatment coverage will be monitored by tracking the total number of children treated in each community as recorded by CHWs during distributions. Denominators for treatment coverage will be estimated through a post-distribution census conducted by trained census workers.

Program costs

Program costs will be captured through micro-costing (units of resources used multiplied by the

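### Delivery Trial II's main coverage analysis takes doses and eligible children from the same health workers' records, so it can overstate coverage, and the protocol names a different denominator elsewhere

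*Protocol*

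**What the plan says.** Protocol 4.5.4.4 defines Delivery Trial II coverage, a secondary outcome, as the "number of doses of azithromycin administered in each community divided by the total eligible population". It lists four ways of obtaining the eligible population: the health workers' own count, a census before treatment, self-report in a survey after treatment, and health-centre administrative estimates. It then ranks them: "The number of eligible children recorded by community health workers will be used for the main analysis". The remaining three serve for sensitivity analysis, and a further analysis sets all four against each other. It gives no reason for the ranking.

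The numerator has the same source. Under the Trial II primary outcome, cost per dose (4.5.4.3): "Doses delivered will be recorded by community health workers using paper data collection forms".

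Protocol 4.5.8.2, which describes measurement for the Delivery Trial, says: "Denominators for treatment coverage will be estimated through a post-distribution census conducted by trained census workers". That sentence does not separate Trial I from Trial II, although the same paragraph does separate them on how dose is determined.

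In Delivery Trial I, coverage is the primary outcome, and doses are "divided by the eligible population as determined by a post-distribution census in each community after a single distribution" (4.5.4.1).

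**The concern.** Coverage is meant to show how much of the total eligible population was reached. If the workers who give the doses also supply the count of eligible children, a child they never meet can fall out of both. The ratio then describes uptake among recorded children, and the reach of the programme drops out of it.

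Two things are at stake. The level of coverage may be too high. The comparison between arms may also be wrong if recording is less complete in one arm. That is plausible, because the workers look for different age groups in the two arms (4.5.3.1) and are not masked (4.5.3.3). The executive summary names coverage, alongside costs, as what Trial II compares between age strategies.

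Separately, 4.5.4.4 and 4.5.8.2 give different denominators for the same quantity, so the text does not settle which figure is the main result.

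**Working it through.** The documents give no coverage figure, assumed coverage or power for this outcome, so there is nothing of the plan's own to reproduce. The check is algebra plus a labelled illustration.

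**Notation.** Let *c* be true coverage (doses to eligible children divided by all eligible children), and *u* the share of eligible children neither recorded nor dosed by the health workers. Neither is given in the documents. I assume *c* of 60% or 80% and *u* from 0 to 20%.

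**Level.** The health-worker denominator is (1 − u) times the true one and the numerator is unchanged, so

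reported coverage = c / (1 − u).

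| True coverage c | u = 0 | u = 5% | u = 10% | u = 20% |
|---|---|---|---|---|
| 60% | 60.0% | 63.2% | 66.7% | 75.0% |
| 80% | 80.0% | 84.2% | 88.9% | 100.0% |

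At 80% true coverage the overstatement is 0, 4.2, 8.9 and 20 points.

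**Arm comparison, no true difference.** With c = 80% in both arms:

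- u = 10% and 5%: 0.80/0.90 − 0.80/0.95 = 0.889 − 0.842 = 0.047, a spurious 4.7 points.
- u = 15% and 5%: 0.80/0.85 − 0.80/0.95 = 0.941 − 0.842 = 0.099, a spurious 9.9 points.
- u equal in both arms: difference 0.

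The sign depends on which arm records less completely; the documents do not tell us.

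**Arm comparison, true difference.** Write c = r × t, where r = 1 − u is the share recorded and t the share of recorded children who are dosed. The health-worker ratio estimates t alone. If t is the same in both arms, a true difference of t × (r₁ − r₂) is missing from the main estimate. Assuming t = 97%, with r = 80% in one arm and 90% in the other, the main analysis shows 97% in both, while census coverage is 0.97 × 0.80 = 77.6% and 0.97 × 0.90 = 87.3%.

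**Opposite direction.** If workers list an extra share *o* of ineligible children whom they do not dose, reported coverage is c / (1 + o). At c = 80% this is 76.2% for o = 5% and 72.7% for o = 10%.

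**The two sections side by side.** Section 4.5.4.4 makes the health-worker count the main denominator, and the census it lists is pre-treatment. Section 4.5.8.2 uses a census for the Delivery Trial, and that census is post-distribution. For Trial II they disagree on the source of the denominator and on the timing of the census.

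**The case against.** Much can be said for the plan.

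- **Every household is to be visited.** Both Trial II arms use door-to-door delivery (4.5.3.1), for which 4.5.8.2 states "CHWs will visit every household in the community". If that is achieved and every eligible child is recorded, u is zero and so is the bias. This stands as a reason for conditional wording. It does not justify the choice, because coverage is there to test whether the plan was carried out.
- **Other denominators are already planned.** The sentence that ranks the methods also prespecifies the census as a sensitivity analysis and a comparison of all four. A reader might infer that a difference in recording between arms would be hidden entirely; it would not be. It would be missing from the main estimate but visible in those analyses.
- **Coverage is secondary.** Cost per dose, the primary outcome, has no eligible-population denominator and is unaffected by this point. This stands and limits the weight of the issue.
- **Trial I is a different trial.** A reader might infer that 4.5.4.1 contradicts the Trial II rule. It does not: it governs another trial, in which coverage is primary and fixed-point is compared with door-to-door delivery. The conflict is between 4.5.4.4 and the general sentence in 4.5.8.2.
- **A document is missing.** The supplied SAP says the Delivery Trials have an SAP of their own, which was not available. It may define the health-worker count or justify its use.

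**Conclusion.** The point holds in conditional form. The main Trial II coverage estimate uses a denominator from the same source as its numerator. It can overstate coverage by the factor 1/(1 − u), and can bias the arm comparison if u differs by arm. In the illustration, which rests on an assumed 80% true coverage in both arms, the spurious difference is 4.7 points for u of 10% versus 5% and 9.9 points for 15% versus 5%. The true u is unknown and may be zero.

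A reader might go further and infer that coverage is overstated, or driven to 100% whatever the reach. The documents do not support that. They do not say how the workers compile their count, recorded children who are not treated still lower the ratio, and over-listing would reverse the bias.

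The conflict between 4.5.4.4 and 4.5.8.2 does not depend on any assumption and needs correcting in either case. It does not by itself show which denominator should be the main one; the case for the census rests on the shared-source problem.

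**What to change.** In 4.5.4.4, make the denominator described as "using a pre-treatment census of eligible children" the main one, and move the health-worker count to the sensitivity analyses. Keep the four-method comparison. Amend 4.5.8.2 so that both sections name the same census for Trial II, stating that it is pre-treatment while Trial I uses a post-distribution census. Carry the same wording into the Delivery SAP. Because the two trials' censuses would still differ in timing, their coverage figures should not be presented as directly comparable on the strength of this change. The protocol should also say who conducts the pre-treatment census, whether it covers all 80 communities, and how long before treatment it takes place; none of this is stated.

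If the health-worker count is kept as the main denominator, give the reason and still correct 4.5.8.2.

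The cost is wording, since the census is already among the planned denominators. Reported coverage may be lower, and the census may be slightly out of date by the time of treatment.

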4.5.5. Sample size

Please refer to Section 4.4.5.1.

4.5.6. Recruitment

Before implementation begins in a region, a sensitization campaign will inform local health authorities and community leaders of the study design and nature of participation in the trial. In addition to IRB and national-, regional-, and district-level approval, community-level approval will be obtained before study activities begin in any community. All households will be recruited for participation in the census, and all children 1–11 or 1–59 months of age will be recruited for the intervention depending on the study arm their community has been randomized to. Household-level consent will be obtained for the census activities, and caregiver/guardian consent will be obtained for interventions and sample collection. Details of informed consent are found in Section 5.3.

